Study title: Effects of virtual reality on cardiorespiratory fitness test results

IRB approval number: 2130870

Document date: 2/21/2024

Protocol Title:

Effects of virtual reality on cardiorespiratory fitness test results

Participants

A power analysis using G*Power version 3.1 will be conducted to determine sample size adequacy. We anticipate a moderate-large effect ($d = 0.7$) of VR on physiological outcomes based on past studies using similar designs (Rutkowski et al., 2021). With an alpha level of .05 and a power level of .80, an estimated 19 participants will be needed to observe a significant effect on $\dot{V}O_{2\text{peak}}$.

To account for participant dropout and missing data, we will recruit an additional 5 participants for a total of 24 participants. The primary means of participant recruitment will be the posting of approved informational flyers throughout the Forrest Hills, Summerville, and Health Science campuses of Augusta University. A secondary means of recruitment will be word-of-mouth. Approved study fliers will also be shared with other instructors at the affiliated institution so that they may announce the study opportunity to their students and share the flier on learning management systems.

Healthy men and (non-pregnant) women 18 years and older will be recruited to take part in this study. Prospective participants will be operationally defined as “healthy” according to results of the 7-item Physical Activity Readiness Questionnaire [PAR-Q; Warburton et al. (2019)]. Answering “yes” to any of the risk assessment questions will result in exclusion from study participation.

Research design

A repeated-measures crossover design will be used in which healthy participants complete a familiarization session and two experimental trials. Experimental days consisted of a maximal graded exercise test with (VR) and without (Control) the use of the immersive VR program separated by at least 1 week. The order of the conditions on the experimental trial days will be counterbalanced and randomized. Cardiometabolic data and psychological responses will be collected during the exercise tests to address the aims of the study. This study will be approved by the associated Institutional Review Board (project 2130870). Written informed consent for each participant will be obtained prior to their participation.

Instruments

A stadiometer and scale (Continental Scale Corp., Bridgeview, IL, USA) were used to measure height and weight of participants. Body composition will be assessed using the InBody 570 bioelectrical impedance analysis device (InBody Co., Ltd, Seoul, South Korea). Participants removed socks and shoes before stepping onto the device. Body composition analysis will be performed according to manufacturer specifications. HR will be measured using a Polar H10 monitor (PolarElectro, Kempele, Finland), a valid and reliable instrument for measuring HR with strong agreement with the electrocardiogram (Schaffarczyk et al., 2022). The H10 monitor is worn on an adjustable belt secured at the xiphoid process over the skin as specified by the manufacturer.

All exercise will be completed on a Velotron cycle ergometer (SRAM, Chicago, IL) which will be paired with software for the investigator to control the intensity (CompuTrainer Inc., Seattle, WA). Expired gases were analyzed in a metabolic cart calibrated on the day of testing to manufacturer specifications (Parvo Medics TrueOne 2400, Marry, UT) via gas collection apparatus (Hans Rudolph Inc., Shawnee, KS). The Meta Quest 2 virtual reality headset (Meta Platforms, Inc., Menlo Park, CA, USA) will be used to run and display the virtual reality video during the VR condition GXT. The video will be a clip from www.YouTube.com which will be

modified using video editing software Adobe Premiere Pro (Adobe Inc., San Jose, CA) to increase speed at each stage of the exercise test to align optical flow with work rate. The Preferences for and Tolerance of the Intensity of exercise Questionnaire (PRETIE-Q) (Ekkekakis, Hall, & Petruzzello, 2005; Santos & Teixeira, 2023) will be used to assess individual preference for different exercise intensities, information which will be used as a covariate when analyzing maximal exercise test outcomes (Hutchinson et al., 2018). Participants completed the questionnaire digitally via the program Qualtrics on a laboratory computer or personal cell phone.

Ratings of perceived exertion (RPE) were collected using the category-ratio 10-point scale. Affective valence will be assessed with the Feeling Scale. Both of these scales were delivered visually on the VR field of view when measurements were to be taken so that participants would be able to see the scale and associated verbal anchors. Remembered pleasure will be assessed using a visual analog scale after each exercise test has been completed and the VR headset has been removed.

Subsequent analysis of the metabolic data to identify $\dot{V}O_{2\text{peak}}$ and ventilatory threshold will be completed using the software WinBreak, version 3.1.

Procedures

Visit 1 - Familiarization

During the initial visit to the laboratory, participants will complete the PAR-Q survey, sign the informed consent if eligibility criteria were met, and then complete the PRETIE-Q. Height, weight, and body composition will be measured and recorded. Instructions for the CR-10 RPE scale and the feeling scale will be explained in detail and understanding will be verified by the investigator.

Once the HR monitor has been donned and it is verified to be working properly, the cycle ergometer will be adjusted to the comfort and preference of the participant. The seat height and handlebar positions will be adjusted until optimized for cycling exercise and the positions will be recorded for the participant's future visits.

The participant will be fitted for the headgear that will be worn during maximal exercise tests on subsequent study visits. Plastic headgear is worn to keep the mouthpiece and gas collection hose in place during exercise so that expired air can be analyzed in the metabolic cart. The entire gas collection apparatus (headgear, mouthpiece, and gas collection hose) will be adjusted and worn for a brief warm-up on the exercise bike. The participant will pedal at a cadence of 50-90 rpm at a work rate of 50 Watts for 3 min. Work rate is adjusted and maintained at all times during exercise with the use of paired software installed on a computer adjacent to the exercise bike (CompuTrainer Inc., Seattle, WA). Responses to the CR-10 RPE and Feeling scales will be solicited at the end of minutes 1 and 3, to which participants will respond with designated hand gestures indicating the appropriate response. This process will be intended to increase the participants' familiarity with the exercise and gas collection equipment, reduce setup complications on future visits, and practice non-verbal communication of psychological scale responses.

An additional exercise stage of 3 min will follow this familiarization warm-up, during which the VR headset will be added to the gas collection apparatus. The participant will be walked through how to start the accompanying VR application and pedal for the designated time to ensure proper fit and function of all pieces of equipment simultaneously. Once this familiarization session is complete, the next visit to the lab will be scheduled and the participant will be directed from the lab.

Visits 2 and 3 – Experimental sessions

The procedures for the two experimental session visits will be the same, aside from the use of the VR equipment in one of the visits. The order of the visits (control and VR) will be counterbalanced and randomized prior to the study commencement. Upon arrival to the lab, participants verbally confirmed that they had abstained from alcohol and strenuous exercise for the previous 24 hours and attained at least 6 hours of sleep the night prior to the visit. They will don the HR monitor, review the psychological scales, and adjust the exercise bike as needed. The gas collection apparatus will be donned and the collection tube will be connected from the mouthpiece to a metabolic cart that has been previously calibrated to the manufacturer specifications. The participant will sit on the exercise bike seat and, once ready, pedal against no resistance for 3 minutes as a warm-up. The exercise test will begin after the warm-up by increasing the resistance to 50 W and increasing the work rate by 25 W each minute thereafter until the termination of the exercise test (Bird et al., 2019). RPE and affective valence responses will be collected at the end of every odd numbered minute (end of minutes 1, 3, 5, etc.). Heart rate will be collected continuously and monitored throughout the test. See Figure 1 for visual timeline of data collection.

The test will be terminated upon volitional exhaustion (when the participant feels that they can no longer continue), when the participant fails to maintain cadence > 50 rpm for longer than 10 s, or when a plateau in $\dot{V}O_2$ (<100 ml/min increase with an increase in work rate) is observed (Poole, Wilkerson, & Jones, 2008). A cool-down period of 3 min at 0 W (no resistance) will immediately follow the termination of the exercise test. At the end of the cool-down, participants will complete the remembered pleasure scale. This will mark the end of the visit and the participant will be directed from the lab.

The experimental session visit which for which the VR equipment is used will be identical in all ways to the control condition, with the exception that the VR headset will be worn in addition to the other previously mentioned equipment. A video displaying natural scenery from the viewpoint of a cyclist will be viewed by the participant throughout the exercise test. Once both experimental visits have concluded, the participants' participation in the study is complete.

Figure 1. Data collection timeline during exercise tests

	Stage of Exercise Test											Cool down	
	Warm-up	1	2	3	4	5	6	7	8	9	10		
Work Rate (W)	0	50	75	100	125	150	175	200	225	250	275	...	0
Duration (min)	3	1	1	1	1	1	1	1	1	1	1	1	3
HR	X	X	X	X	X	X	X	X	X	X	X	X	X
Metabolic data	X	X	X	X	X	X	X	X	X	X	X	X	X
Affective Valence	X	X		X		X		X		X		X	
RPE	X	X		X		X		X		X		X	

"X" = measurement taken at this time point

Procedures for risk management

- **Risk of musculoskeletal injury** – The probability of risk will be reduced primarily by excluding high-risk individuals from participation in the study via the PAR-Q screening questionnaire. Participants will also have a sufficient warm-up time built in to the exercise test to minimize the risk of muscle injury. The gradual increase in work rate over the course of the test will also ensure that physiological demands are reasonable and that risk of muscle injury is limited.
- **Risk of lightheadedness and loss of balance** – the research team members will be standing adjacent to the participant during the exercise test on either side of the equipment to prevent the participant from falling off of the bike in the event of excessive fatigue and shortness of breath during and following the exercise. The investigator will also emphasize that the participant is able to terminate the test at any time for any reason, including severe shortness of breath or lightheadedness, simply by ceasing to pedal on the bike. A sufficient cool down period (3 minutes of cycling at no resistance) will be used to prevent blood from pooling in the veins of the lower body and ensure that blood circulation to the brain and the rest of the body continues after the exercise test has ended.
- **Dehydration** – an unopened bottle of drinking water will be made available to the participant at the start of the study. The participant will be allowed to drink *ad libitum* before and after the exercise test. Drinking water during the test is not possible when the facemask is being worn for data collection purposes.
- **Muscle soreness** – some muscle soreness after a maximal exercise test is unavoidable, but the discomfort participants might encounter will be reduced by ensuring participants have a cool down period after the test.

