Study title: Effects of virtual reality on cardiorespiratory fitness test results

IRB approval number: 2130870

Document date: 6/7/2024

Statistical Analysis Plan

Analysis of data will be completed with SPSS version 29, applying an alpha level of .05. All data will be screened for data entry errors, outliers (difference scores >3.29 standard deviation units from the mean difference score between the two conditions), normality, and homogeneity of variance before formal analysis.

The primary outcome variables $\dot{V}O_{2\text{peak}}$ and workload at ventilatory threshold will be compared between conditions (Control and VR) using separate one-way repeated-measures ANCOVAs (analysis of covariance), with preference for exercise intensity subscale of the PRETIE-Q (Ekkekakis et al., 2005) as the covariate.

The secondary outcome measures of peak power, total test time, % $\dot{V}O_{2\text{peak}}$ at ventilatory threshold, heart rate (HR) at $\dot{V}O_{2\text{peak}}$, HR at ventilatory threshold, respiratory exchange ratio (RER) at $\dot{V}O_{2\text{peak}}$, and RER at ventilatory threshold will similarly be compared between conditions using a series of repeated-measures ANCOVAs with preference for exercise intensity subscale of the PRETIE-Q as the covariate.

Rating of perceived exertion (RPE) and affective valence will be analyzed with separate linear mixed-effects model analyses. Individual participants will be specified as the correlated random effect. The fixed factors will be timepoint and condition.

Results of ANCOVAs will be accompanied by partial eta squared (η^2) as a measure of effect size (small = 0.01; medium = 0.06; large = 0.14). Linear mixed-effect analysis results will use Cohen's d as a measure of effect size (small = 0.20; medium = 0.50; large = 0.80).

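### No masking to condition is described for the post-test WinBreak analysis that yields both primary outcomes; coding the files would reduce reader bias, mainly in workload at ventilatory threshold

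*Protocol*

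**What the plan says.** The Protocol, under Instruments, places the determination of VO2peak and the threshold after the tests: work on VO2peak and "ventilatory threshold will be completed using the software WinBreak, version 3.1". That is all it says about the step. The reader, the number of readers, automatic or visual detection, the averaging window, the handling of aberrant breaths and masking are not mentioned.

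The SAP names two primary outcomes, VO2peak "and workload at ventilatory threshold will be compared between conditions (Control and VR) using separate one-way repeated-measures ANCOVAs". Its data checks begin "All data will be screened for data entry errors, outliers" and go on to normality and variance. It adds no masked reading, file coding or second reader.

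Condition is plain to everyone in the room. Under Visits 2 and 3 the VR visit matches the control visit "with the exception that the VR headset will be worn in addition to the other previously mentioned equipment". Under Procedures for risk management, "the research team members will be standing adjacent to the participant during the exercise test".

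**The concern.** Participants and test staff cannot be masked to a headset. The stored gas-exchange files can be: they are analysed later, and the values taken from them do not depend on knowing the condition. A plan that does not mention masking leaves open that the people who ran the tests also read the files knowing which is which.

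Each participant supplies one VR file and one Control file, and the analysis compares them within person. If the accepted threshold moves by a few watts according to condition, the whole movement goes into the paired difference. Counterbalanced order does not cancel it, because the shift follows the condition and not the visit. The SAP's outlier rule (difference scores more than 3.29 SD from the mean difference) would not show it either. A uniform shift moves the mean and leaves each deviation from it unchanged.

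Workload at threshold is the more exposed outcome, since a breakpoint has to be located. VO2peak is a peak of measured values. With a fixed averaging rule it leaves little to judge, though the plan states no such rule. Secondary outcomes defined at the threshold (percentage of VO2peak, heart rate and RER) depend on the same located point.

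**Working it through.** **The plan's own figure.** Inputs from the Protocol, Participants: d = 0.7, alpha 0.05, power 0.80, 19 evaluable, 24 recruited. Take d as the standardized paired difference and use a two-sided paired t-test with noncentrality d × √n on n − 1 degrees of freedom. Power is 0.799 at n = 18 and 0.823 at n = 19, so 19 reproduces. Adding 5 gives 24, and power is 0.907 if all 24 complete. Masked reading changes none of these figures.

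**Size of the exposure.** The documents give no SD for the paired difference in threshold workload and no size for reader bias, so both are assumed.

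- Systematic shift: 2.5 W or 5 W. Work rate rises 25 W per stage (Visits 2 and 3), so 5 W is 5/25 = one fifth of a stage.
- Paired-difference SD: 15, 20, 25 and 40 W.
- True VR effect: none.
- Standardized shift: dz = shift/SD. Noncentrality: dz × √n.
- False-positive rate: P(|T| > t(0.975, n − 1)), with T noncentral t. The critical value is 2.101 at n = 19 and 2.069 at n = 24.

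Worked case: 5 W with SD 20 W gives dz = 0.25. At n = 19 the noncentrality is 0.25 × √19 = 1.09, and the rejection rate is 17.8% instead of 5%.

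| Shift | SD | dz | n = 19 | n = 24 |
|---|---|---|---|---|
| 2.5 W | 15 W | 0.167 | 10.6% | 12.3% |
| 2.5 W | 20 W | 0.125 | 8.1% | 9.0% |
| 2.5 W | 25 W | 0.100 | 7.0% | 7.6% |
| 2.5 W | 40 W | 0.063 | 5.8% | 6.0% |
| 5 W | 15 W | 0.333 | 28.0% | 34.7% |
| 5 W | 20 W | 0.250 | 17.8% | 21.7% |
| 5 W | 25 W | 0.200 | 13.1% | 15.6% |
| 5 W | 40 W | 0.125 | 8.1% | 9.0% |

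A 2.5 W shift therefore gives about 6 to 12%, and a 5 W shift about 8 to 35%. For a given shift and SD, the rate is higher at 24 than at 19, because a larger sample estimates the bias more precisely. A 1 W shift would hardly matter: at n = 19, 5.9% with SD 15 W and 5.5% with SD 20 W.

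The table uses a paired t-test, not the planned ANCOVA with the PRETIE-Q covariate, and applies to workload at threshold only. There is no corresponding figure for VO2peak.

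**The case against.** The strongest objection is that the documents are silent, and silence is not evidence of unmasked reading. A reader might infer that files labelled by condition will be read by the test staff. Nothing in either document says so, and all that can be stated is that no masking is described. This stands.

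A second objection is that discretion is assumed. If WinBreak is run with fixed settings and its output is accepted, there is little for a reader to shift. The documents do not say whether this is so. This stands as a condition on the size of the problem; it does not close the gap, because no detection or averaging rule is given.

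Third, a reader might treat both primary outcomes as equally exposed, or suppose that any bias would favour VR. Neither is supported. VO2peak leaves far less to judge, and the Participants section anticipates an effect of d = 0.7 without giving its direction.

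Fourth, a reader might infer that coding the files would make the primary outcomes free of bias. It would not. Under Visits 2 and 3, "The test will be terminated upon volitional exhaustion (when the participant feels that they can no longer continue", on loss of cadence, or when a plateau of less than 100 "ml/min increase with an increase in work rate) is observed". Effort and the plateau call occur with the condition in view, before any file is read. For VO2peak this is the more likely route of bias.

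Fifth, the file analysis is not the only step that could be masked. The SAP's screening could also be run under coded condition labels.

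Finally, the upper figure of 35% is the least favourable corner of an assumed grid. At SD 25 to 40 W the same shifts give 5.8 to 15.6%.

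**Conclusion.** The point holds as a gap in bias control. It is not a numerical error or a contradiction, and the sample size and alpha are unaffected. Both primary outcomes come from a post-test analysis for which no masking is described, and masking that analysis is feasible and nearly free. The weight falls on workload at ventilatory threshold, in proportion to the reader's discretion, which the documents do not state. The false-positive rates of about 6 to 12% and 8 to 35% show sensitivity under assumed shifts and SDs. They do not show that bias will occur. The change should be made, but its absence would not invalidate the trial.

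**What to change.** Add to the Protocol, Instruments, next to the WinBreak sentence:

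- Before analysis, each metabolic file is renamed with a random code that hides participant, visit and condition. A script does this, or a team member who does not read the files.
- The same threshold-detection and averaging settings, stated in the plan, are applied to every file.
- Threshold and VO2peak values are locked under the code, and the condition key is merged only afterwards.

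Add a sentence acknowledging that influences during the test (effort, and the plateau call that ends it) remain unmasked. If coding or fully automatic detection is already the practice, saying so is enough.

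Cost: a few minutes per file for at most 24 × 2 = 48 files, and a key to keep. Renaming and reading must be kept apart if a person does the renaming. No visit, procedure, sample size or alpha changes.

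### One VO2 rise below 100 ml/min ends the test as a plateau, with no averaging window or confirmation, so noise can put a submaximal value into the primary VO2peak analysis

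*Protocol*

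**What the plan says.** The graded test is a ladder, described as "increasing the resistance to 50 W and increasing the work rate by 25 W each minute thereafter until the termination of the exercise test" (Protocol, Procedures, Visits 2 and 3 – Experimental sessions). The same section lists three alternative ways for it to end: exhaustion, loss of cadence, "or when a plateau in $\dot{V}O_2$ (<100 ml/min increase with an increase in work rate) is observed". That parenthesis is the whole definition of a plateau. It names no averaging interval for VO2, no earliest stage, no repeat of the low rise and no supporting sign of maximal effort.

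VO2peak and ventilatory threshold are then identified after the test; the Instruments section says this "will be completed using the software WinBreak, version 3.1". No rule is given for judging whether a test was maximal.

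In the SAP (second paragraph), VO2peak and workload at ventilatory threshold are the primary outcomes and "will be compared between conditions (Control and VR) using separate one-way repeated-measures ANCOVAs". Heart rate and RER at VO2peak are secondary outcomes and are not used as effort checks. The one relevant data screen (SAP, first paragraph) concerns difference scores more than 3.29 SD from the mean difference; the SAP does not say what happens to a flagged value.

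On sample size, the Participants section says that "an estimated 19 participants will be needed to observe a significant effect on" VO2peak, at d = 0.7, alpha .05 and power .80. The recruitment target is 24.

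**The concern.** The plateau criterion is meant to recognise that VO2 has stopped rising. As worded, it is met the first time one 25 W step shows a rise under 100 ml/min, at any point on the ladder. Each comparison is a difference between two noisy readings, and it is made at every step. A normal submaximal step clears the threshold only by a margin of the same order as plausible noise.

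This is a different matter from a true plateau cutting short test time or peak power. When the plateau is false, VO2peak itself is wrong, and later software processing cannot recover stages that were never ridden. Such a stop puts an error of several hundred ml/min into one side of a participant's VR-minus-Control difference. If it comes before ventilatory threshold, the other primary outcome is lost as well. With 19 to 24 pairs, a few such errors can dominate the variance.

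**Working it through.** **The plan's own figure.** A two-sided paired t-test with d = 0.7 and alpha .05 gives power .823 at n = 19, so the stated 19 reproduces. That calculation has no allowance for false stops.

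**Inputs.** From the documents: 25 W steps of 1 min from 50 W; threshold 100 ml/min; n = 19; d = 0.7. Assumed, because the documents give no values: VO2 gain 10 ml/min per watt (range 9 to 11); reading SD *s* of 30 to 75 ml/min; seven submaximal steps; SD of true differences 150 ml/min.

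**One step.** The expected rise is 25 × 10 = 250 ml/min (225 to 275 over the range). With independent noise, the difference of two readings has SD √2 × *s*, so

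P(false plateau at one step) = Φ((100 − 250) / (√2 × *s*)).

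At *s* = 50 this is Φ(−150 / 70.7) = Φ(−2.12) = 1.7%. Over seven steps, 1 − (1 − 0.017)^7 ≈ 11%.

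| Reading SD (ml/min) | One step | At least one in 7 steps |
|---|---|---|
| 30 | 0.02% | 0.1% |
| 40 | 0.4% | 3% |
| 50 | 1.7% | 11% |
| 60 | 3.9% | 24% |
| 75 | 7.9% | 44% |

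**Correlated noise.** If errors in adjacent stages have correlation ρ, the SD of the difference is *s* × √(2(1 − ρ)). At *s* = 50:
- ρ = .3: SD 59.2, Φ(−2.54) = 0.56% per step, 3.9% over seven steps.
- ρ = .5: SD 50, Φ(−3.00) = 0.13% per step, 0.9% over seven steps.

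**An example.** Take true values of 1500 and 1750 ml/min at 150 and 175 W, with errors of +80 and −75. The readings are 1580 and 1675, a rise of 95. The test ends at 175 W with about 1675 ml/min, whatever the participant could still have reached.

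**Effect on power.** Simulations of the ladder used a 45 s VO2 lag, last-30-s stage means and capacity of about 9 stages (SD 1.5). A paired t-test stood in for the ANCOVA. At *s* = 50 with independent noise, about 7% to 9% of tests stop early, with VO2peak low by about 870 to 960 ml/min on average. The assumed true mean difference is only 0.7 × 150 = 105 ml/min. Power at n = 19 with independent noise and no outlier screen, as a range over separate simulations:

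| Reading SD (ml/min) | Power |
|---|---|
| 30 | .78 to .82 |
| 40 | .56 to .62 |
| 50 | .19 to .28 |
| 60 | .10 to .14 |

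At *s* = 50, removing pairs beyond 3.29 SD gives about .27. With adjacent-stage correlation, power is about .46 to .59 (ρ = .3) and .67 to .72 (ρ = .5); the lower figure is without the screen and the upper with it.

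A second model (difference SD 200 ml/min, mean maximum 2850 ml/min, independent noise) gave .18 at *s* = 50, against .79 with no plateau stop. The SD of the differences rose from 204 to 599 ml/min.

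**Why the 3.29 SD screen is weak here.** At 8.6% early stops, 19 participants (38 tests) would yield 38 × 0.086 ≈ 3.3 false stops. Suppose *k* of *n* differences carry the same error and the rest are zero. The largest possible standardised deviation is then √((n − k)(n − 1) / (nk)). At n = 19 this is 4.13 for k = 1, which can be flagged, but 2.84 for k = 2, which cannot. Two equal errors in opposite directions give √(18/2) = 3.00, also below 3.29. The errors mask one another. In the second model the screen flagged about 0.7% of pairs at *s* = 50 and almost none at 75.

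**The case against.** **The charitable reading.** The text speaks of a plateau being observed in a maximal test, cites a published criterion that is not reproduced, and has an investigator controlling the work rate. A sensible operator would probably ignore one flat minute at 175 W. That is likely, but nothing written says so. Unwritten discretion, used by staff who can see whether the headset is on, is a reason to write the rule down.

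**Undocumented inputs.** No document gives the reading SD, and independence between stages is a strong assumption. This stands: the same rule is harmless at SD 30 and damaging at SD 50, and correlation removes much of the loss. A reader might infer that power certainly falls far below .80. The documents do not support an unconditional statement.

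**The outlier screen.** A reader might say that the SAP has no safeguard at all. It has one, and it recovers some power, but it is partial and has no stated consequence.

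**Bias against VR.** A reader might infer that the headset makes readings noisier, so that false stops cluster under VR. Nothing in the documents says this. The rule is the same in both conditions, order is counterbalanced, and Visit 1 includes a ride with headset and gas apparatus together to check fit and function.

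**Scope.** When to end a maximal test also bears on participant safety, so a replacement termination rule is not for a statistical review to prescribe. This stands too, and it limits the recommendation to how a plateau is measured, confirmed and analysed.

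**Conclusion.** The concern holds in conditional form. Read as written, one step with a VO2 rise under 100 ml/min ends the test, and the resulting value enters the primary analysis with no check that the plateau was real.

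How much this costs turns mainly on the reading SD and the correlation between stages, both unknown. It is negligible at SD 30 or less. At SD 50 it ranges from severe with independent noise (power about .2 to .3) to modest at correlation .5 (about .67 to .72). Not all of the gap from .80 comes from false stops: at SD 50, even with a confirmed plateau, noise in the scored value leaves power at about .75.

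The expected harm is lost precision in VO2peak, and loss of workload at ventilatory threshold when the stop precedes it. The stated sample size is not miscalculated, and bias against VR is not shown. Because the protocol sets no averaging window, it gives no assurance that the noise is in the harmless range. The point should be fixed; confidence in its size is moderate.

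**What to change.** 1. **Protocol, Visits 2 and 3.** Define how the plateau is measured, with a fixed averaging window per stage, and require confirmation before it counts as attainment of VO2peak. One option to put to the investigators is a low rise on a second consecutive increase. The exact termination wording is theirs to settle. The volitional and cadence terminations are not affected.

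2. **SAP.** Record the reason each test ended. Recheck every plateau-ended test from the stored gas-exchange file, blind to condition, using the fixed window together with the heart rate and RER at peak already collected. Report the primary VO2peak analysis with and without tests whose plateau is not confirmed. State what happens to a difference score flagged by the 3.29 SD screen.

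The cost is a sentence or two in each document and a little more analysis work, with no extra participants or equipment. Under the two-step option, a participant with a real plateau may ride up to about one further 1-min stage, and can still stop at will. In simulation that option brings power at SD 50 back to about .75, not to the full planned figure. The SAP part remains useful after testing is complete, because it works from stored files.
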